9.2.2. Safety Analyses

All safety analyses will be performed on the Safety Sample.

Endpoint	Statistical Analysis Methods
Primary	Our primary outcomes are direct measures related to safety. Our treatments will not be associated with any safety concerns other than the primary outcome that will be analyzed in the treatment efficacy research.
Exploratory	Will be described in the statistical analysis plan finalized before database lock

9.2.3. Other Analyses

We will also evaluate heterogeneous treatment effects (HTE) to better understand whether the treatment effect depends on clinical or socioeconomic features. The overarching goal of the HTE analysis is to identify the factors that can predict if telehealth CIS and OCIC leads to different treatment outcomes compared to the inpatient treatment, which could shed some light on how individual characteristics might influence the treatment response, and pave the way for personalized medicine. The core hypothesis for our HTE analysis is that individual features correlated with poorer adherence with outpatient appointments (e.g., lower socioeconomic status) or psychiatric disturbances associated with poorer prognosis (e.g., severe suicidal thoughts) may at least partially determine who may have better treatment outcomes. The HTE's include three clinical features: 1) Severity of suicidal ideation at baseline and over 180 days; 2) number of suicidal events at baseline only; 3) Substance use at baseline and over 180 days.⁴⁶⁻⁵² The HTE's also include seven sociodemographic features at baseline: 1) Age 2) Gender⁵³⁻⁵⁶ 3) Gender identity⁵⁷⁻⁶⁰ 4) Type of Insurance (public insurance/no insurance/private)⁶¹⁻⁶³ 5) Ethnicity (Hispanic/Non)⁶⁴; 6) Race (African-American (AA) versus non-African American)⁶⁵⁻⁶⁷; 7) Living with one biological parent, two biological parents, a stepparent, a relative, or other.^{68, 69} A past suicide attempt (suicidal event) is one of the strongest risk factors for future suicide attempts and death by suicide in adolescence.^{65, 101-104} Adolescents who attempted suicide are 18 times more likely to attempt suicide compared to adolescents with no prior suicide attempts.¹⁰¹ About 11% of adolescents who attempt suicide will eventually die by suicide. Although female adolescents have a higher rate of suicidal thoughts and attempts, the deaths by suicide are higher for male adolescents.⁵³⁻⁵⁶ In addition, substance use⁴⁶⁻⁵² and gender dysphoria in adolescence substantially increase the risk for suicide.⁵⁷⁻⁶⁰ Type of insurance will allow us to obtain an approximation of income level. Adolescents from lower socioeconomic backgrounds have an

increased risk of serious suicide attempts and suicide.⁶¹⁻⁶³ The cultural context of adolescent suicidal behavior and help-seeking is important and differs among races and ethnic groups.¹⁰⁵ For example, in the Hispanic community, families are much less likely to seek mental health professionals in help seeking and prefer to rely on family first.⁶⁴ Ethnic groups and races differ in rates of adolescent suicidal behaviors.^{105, 106} However, the gap has been decreasing between white adolescent suicides and African American suicides due to an increase in male African American deaths by suicide.⁶⁵⁻⁶⁷ Living situation (living with one biological parent, two biological parents, a stepparent, a relative, or other) is an important HTE for adolescents because living with one parent or the presence of a stepparent was correlated with an increased risk of suicidal thoughts and suicide attempts by adolescents.^{68, 69}

The analysis plan:

To test Aim 1, we will use Cox proportional regression model (CPR) to test whether the telehealth only CIS; outpatient, in-person CIS; and in-patient CIS groups have different incidence rates for recurrent episodes within 3 months. We expect that the sample sizes for the three arms will be *at least* 75, 75, and 70 respectively. To evaluate Aims 2 and 3, we will use the generalized linear model (GLM) to evaluate whether telehealth only CIS; outpatient, in-person CIS; and in-patient CIS groups have different levels of changes in emotional arousal (Aim 2) and treatment satisfaction (Aim 3) at 3 months, after adjusting for several covariates (e.g., age, gender, triage “location”). For CPR, we will have power for our pilot study greater than 0.70 assuming a hazard ratio of 2.8 and greater than 0.8 for our GLM analyses assuming $f^2 = 0.1$ and correcting for multiple comparisons.

The main objective of the analysis plan for the COVID-19 survey is to evaluate whether the changes of levels of emotional dysregulation, anxiety, depressed mood, perceived stress levels, and other indicators of well-being, during the pandemic, are associated with the treatment outcome. Furthermore, we will evaluate whether the changes of these indicators are associated with the perceived level of social support, disruptions in life events, and electronic media habits. First, the changes of levels of emotional dysregulation, anxiety, depressed mood, perceived stress levels, and other indicators of well-being, will be treated as covariates in the analysis under Aims 1-3 (comparative treatment effect analysis). Second, we will then use generalized linear model to evaluate the relationship between continuous outcomes and predictors and ordinal logistic regression model to evaluate the relationship between ordinal outcomes and predictors. The outcomes include the changes of levels of emotional dysregulation, anxiety, depressed mood, perceived stress levels, and other indicators of well-being, and the predictors include perceived levels of social support, disruptions in life events, and electronic media habits.

Interim analysis:

We propose to evaluate the progress of the project at the end of the 6th month. The goal of the interim analysis is to examine the following outcomes: 1) scores from PROMIS Short Form v 1.0-General Life Satisfaction-Short Form 5a (to assess the parent’s well-being), 2) scores from PROMIS Parent-Proxy Life Satisfaction-Short Form 8a, 3) Score from PROMIS Pediatric Life Satisfaction-Short Form 4a, 4) Score from CHRT-SR at baseline and follow-up visits.

Specifically, the change in CHRT-SR scores will be used to facilitate the decisions for revising the protocol. If any of the three treatment groups is found to have statistically significant lower

CONFIDENTIAL

levels of changes in CHRT-SR scores within the first six months with an effect size Cohen's $d > 1.2$ (which is considered as a "very large" effect size according to Sawiloski (2009)¹⁰⁹ in comparison with another treatment group, we will discuss the results with all steering committee members and the DSMB to decide whether we should recommend to psychiatry leadership that the treatment group with overtly inferior treatment outcomes should be discontinued at the four sites.

10. References

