
 Evaluate the safety of CIS-telehealth relative to inpatient and OCIC-in-person among children with similar CHRT scores. 	
 Time to first recurrence of a suicidal event Number of suicidal events Severity of suicidal ideation
Secondary	

 Examine the effectiveness of CIS-telehealth relative to inpatient and in-person OCIC among children with similar CHRT scores. 	
 Score from PROMIS Short Form v 1.0-General Life Satisfaction-Short Form 5a (to assess the parent's well-being) Score from PROMIS Parent-Proxy Life Satisfaction-Short Form 8a Score from PROMIS Pediatric Life Satisfaction-Short Form 4a Score from CHRT-SR at baseline and follow-up visits

 Assess patient and parent treatment satisfaction with CIS-telehealth relative to inpatient and in-person OCIC among children with similar CHRT scores. 	
 Score from Client Satisfaction Questionnaire (CSQ-8)
Tertiary/Exploratory	

 Does Telehealth CIS lead to greater reduction of emotional arousal or perceived stress levels in response to COVID-19 the pandemic 	
 Scores from the COVID-19 survey

CONFIDENTIAL

Overall Design: Observational Design

Number of Participants: CCHMC- 61; other 3 sites- 61 each; total- 244 from all 4 sites

Treatment Groups: Inpatient Psychiatric Treatment vs. Outpatient Crisis Intervention Clinic (OCIC) vs. Telehealth Crisis Intervention Services (CIS)

Duration: 12 Months (1 Years)

2. Introduction

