To address the unmet need of optimizing the treatment and management for adolescent suicidality, we propose to evaluate the effectiveness and safety of telehealth services compared to inpatient and OCIC for suicidal adolescents in our target population. To achieve this goal, we propose a multi- site study to compare telehealth, OCIC, and inpatient care, and see which can lead to a lower risk of a suicidal event (primary outcome) as well as higher treatment satisfaction (TS) and satisfaction with life (SL) (secondary outcomes) of both the legal guardians/parents and patients.^{11, 44, 45} Furthermore, we will assess which clinical and socioeconomic factors at baseline may affect the treatment outcomes. With the results from our proposed study, we will be able to reduce the family and clinician decisional uncertainty about the best treatment setting for suicidal adolescents in our target population. The results will significantly help patients, families, and clinicians with this decision-making process and improve outcomes for suicidal adolescents.

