Breach of confidentiality: There is a potential risk of loss of confidentiality. Consistent with the Federal guidelines, all patients and guardians will be informed of the federally mandated reporting laws for child abuse and neglect, verbally and in the written consent form. Therefore, if abuse or neglect is suspected, per institutional and legal standards and requirements, the Department of Human Services may be called if appropriate and indicated. Risks associated with this reporting include embarrassment, legal consequences, and removal of the child from home.

3. Specific Aims and Hypothesis

Specific Aims	Hypothesis

SA1: Evaluate the safety of CIS-telehealth relative to inpatient and OCIC-in-person among children with similar CHRT-SR scores.
	
 Our working hypothesis is that CIS-telehealth is associated with a greater risk of suicidal event relative to inpatient and in-person OCIC. Response is defined by a delay in first recurrence of a suicidal event and a lower number of suicidal events over 90 days and 180 days. Clinical Features: 
 Severity of suicidal ideation at baseline and over 180 days number of suicidal events at baseline only Substance use at baseline and over 180 days. Sociodemographic features: Age, Gender, Gender Identity, Type of insurance (Public, Private or none), Ethnicity, Race, or living with one biological parent, two biological parents, a stepparent, a relative, or other.

SA2: Examine the effectiveness of CIS-telehealth relative to inpatient and in-person OCIC among children with similar CHRT scores.
	
 Our working hypothesis is that CIS-telehealth will be associated with poorer reduction in emotional arousal and perceived stress levels in response to COVID-19 the pandemic relative to CIS-inpatient and CIS-in-person.

SA3: Assess patient and parent treatment satisfaction with CIS-telehealth relative to inpatient and in-person OCIC among children with similar CHRT scores.
	
 Our working hypothesis is that CIS-telehealth is associated with less patient satisfaction than inpatient and in-person OCIC among children with similar CHRT scores.

Exploratory Aim
	

[figure not shown]
Specific Aims	Hypothesis

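### Two of the ten HTE features, ideation severity and substance use, are also defined by values over the 180 days after treatment starts; those versions cannot predict who does better in which setting, and estimates based on them can be biased in either direction

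*Combined protocol and SAP*

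**What the plan says.** Section 9.2.3 gives the purpose of the HTE analysis as being to "identify the factors that can predict if telehealth CIS and OCIC leads to different treatment outcomes compared to the inpatient treatment", with personalised treatment choice in view. It names ten features. Three are clinical: "1) Severity of suicidal ideation at baseline and over 180 days; 2) number of suicidal events at baseline only", and then "3) Substance use at baseline and over 180 days". The other seven are fixed in time: "The HTE's also include seven sociodemographic features at baseline".

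The table in section 3 repeats the clinical list under SA1, again with "Severity of suicidal ideation at baseline and over 180 days". Section 4.1 says that the CHRT-SR, the Suicidal Event Form and the Clinical Features (CF) form are completed at baseline and every two weeks for the HTE evaluation. Section 8 and the schedule in section 11.1 confirm this two-weekly repetition.

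The synopsis lists these endpoints for the primary safety objective: "Time to first recurrence of a suicidal event Number of suicidal events Severity of suicidal ideation". Follow-up CHRT-SR scores appear there again as a secondary endpoint. Section 2.1 describes the intention as "we will assess which clinical and socioeconomic factors at baseline may affect the treatment outcomes".

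**The concern.** A feature that is to guide the choice of setting has to be known when that choice is made. Under sections 4.1 and 6.1 the clinician assigns the setting at or after the crisis assessment, before the study approaches the family. Ideation or substance use over the following 180 days does not exist at that point.

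The over-180-day versions are also open to two influences that a baseline value escapes. The setting may change them, which is why ideation severity is an endpoint. A suicidal event may change them too, because the scales are completed again every two weeks after it. Grouping patients by such a variable, or interacting it with arm, compares patients selected partly by the treatment and partly by the outcome. In this population, a subgroup result that wrongly suggests the setting makes no difference, or wrongly suggests that it does, could mislead decisions about disposition.

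The authors drew the needed distinction for the event count, which is limited to baseline, but did not apply it to the other two clinical features.

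**Working it through.** **Count of features.** 3 clinical + 7 sociodemographic = 10. Baseline only: 1 (event count) + 7 = 8. At baseline and also over 180 days: 2. Both of those have a usable baseline value.

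**Plan's own figure.** The documents give no effect size, power or model for the HTE analysis, so there is nothing to reproduce. All inputs below are illustrative assumptions.

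**Check 1: subgroup ratios with no true effect modification.** Let B be baseline severity (standard normal), A the arm (0 or 1), and s the share of the arm effect that runs through later ideation M.

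- M = 0.6·B + 0.5·s·A + 0.8·noise
- hazard = exp(−1.75 + 0.69·M + 0.345·(1 − s)·A), followed for one time unit
- The total arm effect on the log hazard is 0.69 × 0.5·s + 0.345·(1 − s) = 0.345 for every s. That is a conditional hazard ratio of exp(0.345) = 1.41.
- Event feedback, where used, adds 0.5 to M after an event.
- Results are event-rate ratios between arms, overall and in the lower and upper halves of a median split.

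The overall ratio is about 1.38 in each case; separate runs differ by about 0.01 to 0.02. With full mediation, the split on baseline severity gives 1.40 and 1.38, which is correct because nothing is modified. The split on M gives:

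- s = 0: about 1.39, so no attenuation
- s = 0.25: 1.32 and 1.35; with event feedback 1.30 and 1.28
- s = 0.5: 1.25 and 1.26; with event feedback 1.15 to 1.19
- s = 1: 1.11 and 1.14; with event feedback 0.94 and 1.04

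The direction can reverse. If the arm lowers M by 0.25 but has a direct harmful effect of 0.345, the overall ratio is 1.18 and the split on M gives 1.32 and 1.31.

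**Check 2: recovering true modification.** This is a Cox simulation with 6,000 patients. True modification by baseline ideation is 0.50 log hazard ratio per SD, later ideation correlates 0.6 with baseline, and later ideation carries 0.7 log hazard ratio per SD.

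- Arm × baseline ideation: estimate 0.46 (0.47 with event feedback)
- Arm × over-180-day ideation: estimate 0.27 (0.14 with event feedback)
- Shortfall against the baseline term: 1 − 0.27/0.46 = 41%, and 1 − 0.14/0.47 = 70%
- Arm × baseline ideation with the 180-day terms in the same model: 0.50 (0.57 with event feedback)

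The over-180-day term understates the modification. The baseline term still recovers it.

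**The case against.** The strongest reply is that little depends on these two extra definitions. Eight of the ten features are baseline only, the other two are also analysed at baseline, and check 2 shows that the baseline interaction survives. A reader might infer that the HTE analysis as a whole cannot find predictors. The documents do not support that.

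A reader might also infer that the plan would hide a real difference between arms. If 180-day ideation were a covariate in the arm model, it could: in a Cox simulation of 70 against 75 patients, with half the effect mediated, a hazard ratio of 2.8 fell to 1.7, or 1.2 with event feedback. But no such model is written. The primary Cox model in section 9.2.1 names treatment option only, and the Aim 1 text in section 9.2.3 adds neither variable. Section 9.2.3 does put changes from the COVID-19 survey into Aims 1 to 3 as covariates, but that is a separate matter.

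Nor is the bias always towards no difference. It vanishes without mediation and reverses when the direct and mediated effects oppose each other.

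Three further points stand in part. Section 9.2.3 gives no HTE model and section 9.2 defers the detailed analysis plan, so the use of the 180-day values could still be settled there. Deferral does not cure the wording, though, because three sections already assign post-baseline measures to the HTE analysis. The HTE analysis is secondary and weak: the section 9.1 rates imply 70 × 0.19 + 75 × 0.10 = 20.8 events for inpatient against OCIC, and simulated power for a baseline interaction of 0.50 to 0.69 was only 14% to 26%. Finally, section 2.1 is a single sentence of rationale that does not mention effect modification. It is looser wording, not a firm contradiction of section 9.2.3.

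**Conclusion.** The point holds for the over-180-day versions of two features. They are measured after treatment starts, can be affected by the setting and by the event, and are unknown at the crisis assessment. They cannot serve the purpose that section 9.2.3 sets, whatever the size of the bias. This is a stated choice, repeated in SA1 and supported by section 4.1, and not merely a missing detail.

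The size of the bias is not fixed by the documents. It depends on how much of the arm effect runs through ideation or substance use, and on whether events raise later scores. The simulated subgroup ratios run from about 1.39 down to about 0.94 against an overall 1.38, and above the overall ratio when the effects oppose. These figures rest on the assumed inputs and show possible size, not a forecast. What is at risk is the secondary subgroup and interaction results that use the 180-day values. The primary comparison and the baseline HTE results are not.

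**What to change.** - In section 9.2.3 and in SA1 of section 3, define all HTE modifiers by baseline values only: baseline CHRT-SR for ideation severity and the baseline CF form for substance use. Remove the 180-day wording from the modifier list.
- In section 4.1, say that only the baseline values serve the HTE evaluation. As written, that sentence also covers the two-weekly Suicidal Event Form, although section 9.2.3 limits the event count to baseline.
- Report 180-day ideation and substance use by arm as outcomes.
- In the analysis plan, write the arm-by-feature interaction model. State which record counts as baseline, since section 4.1 allows the CF form up to 72 hours after admission.

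This also brings the text into line with section 2.1. The cost is protocol and SAP wording only: the schedule in section 11.1 already collects both baseline values, and the two-weekly data stay in use as outcomes. The change should be made before the analysis plan is finalised.

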4.2. Number of Participants

We proposed to recruit approximately 244 eligible cases that will be placed in 3 treatment arms: inpatient, in-person OCIC and telehealth CIS. We expect to recruit a small proportion of the suicidal adolescent group in the ED or who receive crisis assessment from telehealth or via phone. To test Aim 1, we will use Cox proportional regression model (CPR) to test whether the telehealth only CIS; outpatient, in-person CIS; and in-patient CIS groups have different incidence rates for recurrent episodes within 3 months. We expect that the sample sizes for the three arms will be *at least* 75, 75, and 70 respectively. To test Aims 2 and 3, we will use the generalized linear model (GLM) to evaluate whether telehealth only CIS; outpatient, in-person CIS; and in-patient CIS groups have different levels of changes in emotional arousal (Aim 2) and treatment satisfaction (Aim 3) at 3 months, after adjusting for several covariates (e.g., age, gender, triage “location”). For CPR, we will have power for our pilot study greater than 0.70 assuming a hazard ratio of 2.8 and greater than 0.8 for our GLM analyses assuming $f^2 = 0.1$ and correcting for multiple comparisons.

Recruitment Plan for Prospective Studies

. Estimated number of potentially eligible study participants	500
. Total number of study participants expected to be screened:	300
. Total number of study participants expected to be eligible of those screened:	270
. Target sample size (use same number stated in milestones):	244
. Total number of practices or centers that will enroll participants:	4
. Projected month first participant enrolled (month after project initiation):	2nd Month

• Projected month last participant enrolled (month after project initiation):	10 th Month
• Projected rate of enrollment (anticipated number enrolled per month of enrollment period):	2- 10/month
• Estimated percentage of participant dropout:	10%

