5.7. Screen Failures

Screen failures are defined as participants who consent to participate in the clinical study but are not subsequently included in the study. A minimal set of screen failure information is required to ensure transparent reporting of screen failure participants to meet the Consolidated Standards of Reporting Trials (CONSORT) publishing requirements and to respond to queries from regulatory authorities. Minimal information includes demography, screen failure details, eligibility criteria, and any serious adverse events (SAE).

Individuals who do not meet the criteria for participation in this study (screen failure) may be rescreened. Rescreened participants will be assigned the same participant number as for the initial screening.

6. Treatments

Study treatment is defined as psychiatric treatment within either Outpatient Crisis Intervention Clinic (OCIC), on an Inpatient unit, or telehealth crisis intervention services. Participants will be placed in the treatment setting by the assessing clinician. These therapeutic interventions are available whether or not the subject agrees to participate in the study.

Telehealth crisis intervention services (telehealth CIS) is defined as psychiatric services provided via telehealth services that is expected to be scheduled within 7 business days of the crisis assessment. Interventions can be with a social worker, therapist or psychiatrist. Services are not in person and occur over a computer video/phone system.

Inpatient treatment includes supportive individual therapy, improving patient's coping skills, family meetings about safety planning, and medication management.^{6-9, 81}

OCIC services include crisis psychotherapy/intervention, evidence-based screening/risk assessments, coordination of care/referral to an ongoing provider, short-term therapy/crisis treatment, safety planning, and/or referral and linkage to follow-up care. Treatment in OCIC may include group therapy, individual therapy, and/or family therapy, depending on the site. Please

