6.1. Method of Treatment Assignment

All eligible individuals will be followed in three treatment arms: OCIC versus inpatient treatment versus telehealth groups. Potential participants will be identified once they have been assigned to a treatment setting by a licensed clinician at each institution (Cincinnati, Dallas, Columbus, and New York). Research coordinators will be in contact with clinicians who complete the assessments to identify appropriate participants. The CHRT-SR will be reviewed to identify participants who meet study criteria (i.e. need higher level of treatment due to suicidal thoughts). Once a potential participant is identified, research coordinators will contact guardians via phone to introduce the study and complete remote enrollment and consenting procedures.

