9.2.1. Efficacy Analyses

Endpoint	Statistical Analysis Methods
Primary	The primary outcome measure for this proposed research will be the time to first recurrence of a suicidal event. We will examine if the treatment option can predict the “time to the first suicidal event” using the Cox-proportional hazard model.
Secondary	The secondary outcome is Satisfaction with Life (SL), which will be measured every two weeks. The treatment effect on such time-series

	data will then be analyzed using mixed-effect ordinary logistic regression model.
Exploratory	Will be described in the statistical analysis plan finalized before database lock

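### The Aim 1 Cox model compares clinician-assigned settings with no stated adjustment for baseline confounders or site, and the only covariates stated for Aim 1 are change scores measured after assignment

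*Combined protocol and SAP*

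**What the plan says.** All references are to the combined protocol and SAP.

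- **Assignment.** Section 6 (Treatments): "Participants will be placed in the treatment setting by the assessing clinician". Section 6.1: "Potential participants will be identified once they have been assigned to a treatment setting by a licensed clinician at each institution".
- **Primary model.** Section 9.2.1: "We will examine if the treatment option can predict the" time to the first suicidal event, by Cox regression. Section 9.2.3 gives the Aim 1 version, "To test Aim 1, we will use Cox proportional regression model (CPR) to test whether the telehealth only CIS", in-person outpatient and inpatient groups differ within 3 months. Section 4.2 repeats it. None of these sentences names a covariate.
- **Aims 2 and 3.** The sentence on the generalized linear model in section 9.2.3 does name adjustment: "treatment satisfaction (Aim 3) at 3 months, after adjusting for several covariates", with age, gender and triage location as examples.
- **COVID-19 survey plan.** Later in section 9.2.3, changes in emotional dysregulation, anxiety, depressed mood, perceived stress and other well-being indicators are to be covariates for Aims 1 to 3. Section 8 places the COVID-19 survey at week 2.
- **Baseline features.** Section 9.2.3 uses them for effect modification: "We will also evaluate heterogeneous treatment effects (HTE) to better understand whether the treatment effect depends on clinical or socioeconomic features".
- **Comparability.** Section 3 frames Aim 1 among children whose CHRT-SR scores are similar. Section 5.4 says the baseline score helps to define a consistent group, and reports no difference in score by disposition from November 2019 to March 2020 (F = 0.23, p = 0.7921).
- **Later SAP.** Section 9.2 defers detail to a SAP to be finalised before lock. The topics listed are participant selection and the handling of missing, unused and spurious data.

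**The concern.** In a non-randomised comparison, anything that influences both the clinician's choice of setting and the risk of recurrence distorts an unadjusted hazard ratio. The document supplies candidates for both links. Section 2.2 reports that the older practice parameters favoured inpatient care for attempters whose suicidal thoughts persisted. It also reports that Dallas patients with later events had more previous attempts and higher active ideation at entry. Section 9.2.3 adds: "A past suicide attempt (suicidal event) is one of the strongest risk factors for future suicide attempts". Site is a further candidate, because section 6 describes site-specific care: Dallas OCIC lasts 4 to 6 weeks with group therapy, while New York OCIC is 3 visits.

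Aim 1 is the primary safety question, and section 2 says the results should guide the choice of setting and inform practice parameters. A hazard ratio that mixes setting with who was sent there, and at which site, does not answer it.

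**Working it through.** **1. Can any stated provision act as confounder control for Aim 1?**

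| Provision | What it does | What it leaves open |
|---|---|---|
| Covariates for Aims 2 and 3 (9.2.3) | Adjusts the generalized linear model | Not stated for the Cox model |
| Change scores for Aims 1 to 3 (9.2.3) | Adds changes during the pandemic, tied to a week-2 survey | Not baseline values; treatment or early events may have moved them |
| Heterogeneity analysis (9.2.3) | Tests whether the effect varies by feature | Does not balance the arms |
| Similar CHRT-SR (3, 5.4) | States an intent | No cut-off, matching, weighting or model term; one score only |
| Check by disposition (5.4) | Finds no CHRT-SR difference | Names no telehealth group; silent on prior events and site |
| Later SAP (9.2) | Lists topics to come | Confounding is not among them |

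None supplies adjustment for baseline confounders or site.

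**2. How large could the bias be?** The documents do not say. As an illustration with every input assumed, take no true setting effect and a binary confounder with hazard ratio h and prevalences p1 and p0. The unadjusted ratio is roughly (p1·h + 1 − p1)/(p0·h + 1 − p0).
- 40% vs 30%: h = 2 gives 1.4/1.3 = 1.08; h = 4 gives 2.2/1.9 = 1.16. Reversed: 0.93 and 0.86.
- 60% vs 30%: 1.6/1.3 = 1.23 and 2.8/1.9 = 1.47. Reversed: 0.81 and 0.68.

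**3. The plan's own power.** Section 9.1 gives 0.70 for inpatient vs OCIC at a hazard ratio (HR) of 2.8, 6-month rates of 19% and 10%, and two-sided alpha 0.05. By Schoenfeld's formula, power = Φ(√(D·p(1−p)·(1−R²))·ln HR − 1.96), where D is events, p the share in one arm, and R² the share of variation in setting explained by the covariates (0 if unadjusted).
- 244/3 = 81.3 per arm: D = 81.3 × 0.29 = 23.6, power 0.705. This reproduces the plan.
- The post-dropout 70 and 75: D = 70 × 0.19 + 75 × 0.10 = 20.8, power 0.650.

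**4. Expected events, all three arms (70/75/75).**
- Low, at the plan's 19/10/10%: 13.3 + 7.5 + 7.5 = 28.3 at 6 months. Under constant hazard, 3-month rates are 1 − √0.81 = 0.100 and 1 − √0.90 = 0.0513, giving 7.0 + 150 × 0.0513 = 14.7.
- High, assuming the 27.3% Dallas suicidal-event rate (section 2.2) in every arm: 220 × 0.273 = 60.1 at 6 months; 220 × (1 − √0.727) = 32.4 at 3 months.

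The low rates are for readmission and attempts (section 9.1). The primary event is a composite that also counts interrupted attempts, urgent evaluations and suicide deaths (section 2.2).

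**5. Cost of adjustment, inpatient vs OCIC, HR 2.8, p = 70/145.** R² is not in the documents; 0.2 is assumed.

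| Horizon | Events D | Unadjusted | R² = 0.2 |
|---|---|---|---|
| 6 months, low | 20.8 | 0.65 | 0.56 |
| 6 months, high | 145 × 0.273 = 39.6 | 0.90 | 0.83 |
| 3 months, low | 10.8 | 0.40 | 0.33 |
| 3 months, high | 145 × 0.147 = 21.4 | 0.66 | 0.57 |

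At 6 months, R² from 0.1 to 0.3 gives 0.61 to 0.50 (low) and 0.87 to 0.77 (high). The high rows vary only the event count: equal rates in all arms would not themselves produce a hazard ratio of 2.8.

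**6. Can the events carry the model?** Setting (2 parameters), prior events (1), CHRT-SR (1) and site (3) make 7. That is 28.3/7 = 4.0 to 60.1/7 = 8.6 events per parameter at 6 months, and 2.1 to 4.6 at 3 months. With site as a stratum there are 4 parameters: 7.1 to 15.0 and 3.7 to 8.1. The list must be short.

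**The case against.** The strongest reply is that section 9.2 offers only a summary, with a SAP to follow. Silence there does not show that an unadjusted primary model was chosen. That stands: a reader might infer a decision against adjustment, and the document does not support it. But the topics listed for the SAP do not include confounding, and the same summary does name covariates for Aims 2 and 3.

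A reader might also infer that setting is the only predictor anywhere in the plan for Aim 1. That is too strong, because the COVID-19 paragraph names change scores for Aims 1 to 3. They do not help: they are not baseline confounders, and adjusting for them could remove part of a treatment effect or add bias.

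A third tempting reading is that calendar time confounds the comparison, since telehealth expanded when the pandemic curtailed in-person care (section 2.1). Section 4.2 gives one enrolment window, months 2 to 10, and no arm-specific periods. This is possible, not shown.

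Several passages narrow the gap. Section 5 describes patients who could safely be managed in any of the settings, section 6.1 has CHRT-SR reviewed when participants are identified, and section 5.4 found no difference in score. The narrower population is not an eligibility criterion in sections 5.5 and 5.6, and none of this deals with prior events or site.

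**Conclusion.** The concern holds for baseline confounders and site. For a clinician-assigned comparison, the primary Cox model states neither, and the only covariates stated for Aim 1 are the wrong kind. Enrolment period is a secondary, possible confounder.

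The direction and size of the bias are not established. A reader might expect the bias to count against inpatient care because sicker patients go there, but the document gives no prior-event distribution by arm, and its only comparison of severity by disposition found no difference. The ratios in step 2 of the working are illustrations, not estimates.

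It would also be too strong to say there are too few events to adjust. That reading rests on 28 events at 6 months; the document's own suicidal-event rate points to about 60 if it held in all arms. The conclusion about the missing adjustment depends on neither figure. This should be settled before database lock, because it concerns the primary safety result and prespecification cannot be recovered afterwards.

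**What to change.** Before database lock, write into the SAP:

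1. **Primary Aim 1 analysis.** A Cox model for setting, adjusted for the number of prior suicidal events, baseline CHRT-SR, and site as a stratum or covariate (name one; a stratum saves three parameters). Use values recorded at the crisis assessment where available, since section 4.1 allows baseline forms up to 72 hours after admission. Report the unadjusted model as supportive, and a propensity-score version and enrolment period as sensitivity analyses.
2. **Change scores.** State that the changes in mood, stress and well-being are not in the primary Aim 1 model.
3. **Similar CHRT-SR.** State that this is applied through the CHRT-SR term in the model.

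The cost is SAP wording, analysis work and the loss of precision shown in step 5 of the working. No new data are needed. Confounders that were not measured, or were measured poorly, will remain, and the report should say so.
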